6.2 Schedule of Events

Study Activity	Screening Visit	Procedure	Week 1	Month 1	Month 2	Month 3	Month 4	Month 5	Month 6	Months 7-11	Month 12
Informed consent	X										
History and demographic information	X										
Physical exam ^a	X										
MRE/MRS ^b (magnetic resonance elastography/spectroscopy)	X								X		
One day evaluation in obesity clinic ^c	X										
B-HCG ^d	X										
Endoscopic ultrasound (EUS)		X							X		
EUS guided liver biopsy		X							X		
Placement of intragastric balloon		X									
Daily phone calls life Style Intervention			X								
Monthly group visit health-care coach/nutrition				X	X	X	X	X	X	X	X
Follow-up phone calls by bariatric clinic				X	X	X	X	X	X	X	X
Removal of intragastric balloon									X		
a Weight, height, waist circumference, demographic information b MRE=Magnetic Resonance Elastography, MRS=Magnetic Resonance Spectroscopy c Nutrition, psychology, gastroenterology d Serum pregnancy test (women of childbearing potential)											

6.3 Tissue lipidomics workup

A total of 50 mg of liver tissue will be collected via EUS-guided biopsy. Sharkcore needle is 22 gauge. Diameter is ~0.7 mm. ~270 mm of tissue length will be acquired and will deliver a volume of ~50 mg. The sample will be frozen in liquid nitrogen immediately upon harvesting in the endoscopy suite and placed in a 1.5 conical Eppendorf tube. Samples shall not sit more than few minutes before flash freezing to ensure adequate analysis. Also, inspection before freezing will occur to ensure that the tissue is relatively clean specimen on inspection.

7 Statistical Plan

Baseline subject characteristics will be described by their means, medians and and/or frequencies. For our primary study endpoint of improvement in NASH activity scores on paired liver biopsies at baseline and after 6 months, we will be using a paired t-test with two sided alpha <0.05. With a sample size of 20 subjects, we will have 80% power to detect a medium to large difference in activity scores (0.66). Please see table below for minimum sample size needed for each desired effect size.

	Small effect size 0.5	Medium effect size 0.66	Large effect size 0.8
Sample (N)	34	20	15

Additionally, we will run a linear regression analysis with the change in NASH activity scores as the outcome with baseline BMI and diabetes as the covariates on a univariable and multivariable fashion to investigate their effects on the primary outcome.

For our secondary endpoint of number of subjects with regression of fibrosis in paired liver biopsies, we will be reporting the percentage of subjects with regression. As far as the secondary endpoint of percent total body weight 6 months after Orbera balloon placement, we will be reporting the mean or median percent total body weight loss at 6 months.

For our secondary endpoint of quantifying total fat liver and triglycerides content, we will be reporting the mean and median percent of change at 6 months.

8 Safety and Adverse Events

All adverse events occurring during the study, including those not meeting the criteria of an Unanticipated Adverse Device Effect (UADE) will be recorded on the appropriate case report form. Records of these events will be maintained and reports submitted to the FDA and IRB according to the regulatory requirements. Expected clinical adverse events and nonsignificant (not serious) clinical adverse events will not be reported. Expected clinical adverse events and anticipated adverse device effects are those listed in Section 1.5.2.

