Of note in this protocol will include patients with diagnosis of NASH with fibrosis (stage 1-3) on MRE/MRS (magnetic resonance elastography/magnetic resonance spectroscopy), which has demonstrated high accuracy in making the diagnosis, but has unknown sensitivity and specificity to detect change over time and has no standardized validated criteria to objectively assess improvement in NASH and fibrosis as exists for liver biopsy, which remains the gold standard in clinic trial evaluating the impact of intervention on NASH. **In the rare instance that the MRE result was falsely positive and the patient was not found to have NASH on liver biopsy. The patient will continue with balloon therapy for weight loss, but we will not repeat liver biopsy at 6 months, since the balloon is indicated for obesity with or without NASH with clear health benefits to weight loss in this cohort.** The balloon cost will remain covered by the study under these rare circumstances.

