3.2 Primary Study Endpoint

Number of subjects with ≥ 2 points improvement in NASH activity scores on paired liver biopsies before and 6 months after intragastric balloon placement.

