4.1 Inclusion Criteria

- Age 21 – 70 years
- Male and Female
- BMI between 30 to 55 kg/m²
- NASH with fibrosis (excluding advanced fibrosis or cirrhosis). This is determined by a baseline liver biopsy when available showing stage 1-3 fibrosis, but *not* stage 4 (advance fibrosis or cirrhosis), and / or magnetic resonance elastography (MRE) showing a liver stiffness measurement range that spans a score of ≥ 3.0 kPa and with a mean liver stiffness value of < 5 kPa. Both of these tests are valid for study inclusion within 6 months of enrollment. When both a biopsy and MRE are available prior to study enrollment the fibrosis designation will be based on the gold standard histology.
- Subjects will have attempted and failed more conservative weight reduction alternatives, such as supervised diet, exercise and behavior modification programs (per Orbera’s approved PMA: P140008)
- Able to provide a written informed consent

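### The regression of NAS change on BMI and diabetes should be accompanied by a prespecified model that also includes baseline NAS

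*Combined protocol and SAP*

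**What the plan says.** After the paired t-test, Section 7 (Statistical Plan) adds a "linear regression analysis with the change in NASH activity scores as the outcome with baseline BMI and diabetes as the covariates", fitted in univariable and multivariable form. Its stated purpose is "to investigate their effects on the primary outcome". No section adds baseline NAS to the model.

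The primary endpoint in Section 3.2 is the number of subjects with "≥ 2 points improvement in NASH activity scores on paired liver biopsies before and 6 months after intragastric balloon placement".

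Entry under Section 4.1 rests on BMI and on fibrosis. Fibrosis is staged by an available biopsy and/or by MRE "showing a liver stiffness measurement range that spans a score of" at least 3.0 kPa, with a mean below 5 kPa. No minimum NAS is set. The nearest thing to a floor is in Section 3.1: if the placement biopsy shows no NASH, the patient keeps the balloon, "but we will not repeat liver biopsy at 6 months". Such patients leave the paired data. That is a filter on diagnosis and carries no NAS value.

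By Section 5.2 and the Schedule of Events (6.2), every enrolled subject has a placement biopsy, so every subject with paired data has a baseline NAS.

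**The concern.** The regression is meant to say whether BMI and diabetes affect the outcome. A change score also carries the starting value. If subjects with more disease at the start fall further because they have further to fall, any covariate associated with baseline NAS takes up part of that difference. A diabetes coefficient could then be read as a better response to the balloon when it only records a higher start.

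The association need not exist in the population. With about 20 subjects split by diabetes, a chance gap in baseline NAS of a good fraction of a point is ordinary. The protocol itself describes NAFLD as patchy and biopsy as open to sampling error (Section 1.1), so observed baseline NAS is also noisy.

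At stake is the reading of a supporting analysis that may guide patient selection in a later trial.

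**Working it through.** **The plan's own figure.** Section 7 gives n = 20 for effect size 0.66, 80% power, two-sided 0.05. Exact paired-t power at n = 20 is 79.95% (21 subjects for a strict 80%), so the figure reproduces to rounding. The other entries, 34 and 15, reproduce exactly. None of them uses the regression.

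**Inputs.** From the documents: n = 20 and covariates BMI and diabetes. The only NAS SDs printed in Section 1.1 are end-of-treatment values of 0.75 and 2.25 from the earlier randomised balloon study. Assumed, because the documents give no figure: 10 diabetic and 10 non-diabetic subjects, true baseline NAS mean 4.5 and SD 1.2, biopsy error SD 0.5 to 1.0, between-subject response SD 0.8, whole-number scores, no effect of diabetes itself, and diabetic subjects starting g = 1 point higher.

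**Expected coefficients.** Let k be the proportional fall and r the within-group reliability of the baseline biopsy score.
- r = 1.2² / (1.2² + error²) = 1.44/1.69 = 0.85 at error SD 0.5, and 1.44/2.44 = 0.59 at 1.0.
- Planned model: spurious diabetes coefficient = −k × g (negative means more improvement).
- With baseline NAS added: (1 − k) × (1 − r) × g.

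| Fall in NAS | Planned model | With baseline NAS, error SD 0.5 | With baseline NAS, error SD 1.0 |
|---|---|---|---|
| 35% of start | −0.35 × 1 = −0.35 | 0.65 × 0.15 = +0.10 | 0.65 × 0.41 = +0.27 |
| Same for all (k = 0) | 0 | +0.15 | +0.41 |

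Simulation with whole-number scores agrees. With the 35% fall, the planned model gives about −0.35 and the adjusted one +0.12 to +0.27. With a constant 1.5-point fall, the planned model gives −0.05 to −0.01 and the adjusted one +0.19 to +0.42.

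**Against sampling error.** The SE of the planned diabetes coefficient is about 0.55 to 0.78. The spurious 0.35 is therefore 0.35/0.78 = 0.45 to 0.35/0.55 = 0.64 of one SE.

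**A less favourable set of assumptions.** With true SD 1.5, a 50% fall and the same 1-point gap, the planned model gives about −0.50. Its false-positive rate for diabetes is 15.5%, 12.1% and 7.5% at reliability 1.0, 0.8 and 0.6, against 5.0%, 7.4% and 5.1% with baseline NAS. With a constant fall under the same inputs, the planned model stays at 4.7% to 5.3%.

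**Chance imbalance alone.** With true SD 1.5 and 10 versus 10, the SD of the gap in observed baseline is (1.5/√r) × √(2/10), which is 0.75 at r = 0.8 and 0.87 at r = 0.6. The slope of change on observed baseline is −(1 − (1 − k) × r). At r = 0.8 it is −0.2 (k = 0) or −0.6 (k = 0.5). At r = 0.6 it is −0.4 or −0.7. A one-SD chance gap thus moves the diabetes coefficient by 0.15 to 0.45 points (r = 0.8) or 0.35 to 0.61 points (r = 0.6).

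**Precision.** With a 35% fall, adding baseline NAS cuts residual SD from 1.19 to 1.02 (14%) at error SD 0.5 and from 1.67 to 1.36 (19%) at 1.0. The SE of the diabetes effect falls by 11% to 16% if the groups start level, but by only about 4% to 12% with the 1-point gap.

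**Degrees of freedom.** Residual df go from 20 − 3 = 17 to 20 − 4 = 16.

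**The case against.** The strongest reply is that diabetic and non-diabetic subjects are pre-existing groups, so change score versus baseline adjustment is a choice of question rather than an error. This stands. With a constant fall the planned coefficient is right on average, while the adjusted one is biased by biopsy error. A reader might infer that the adjusted model should replace the planned one. The documents do not support that, because they do not say how the fall relates to baseline.

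A reader might also infer that regression to the mean biases the planned coefficients systematically. It does not when the true fall is the same for all. What remains is chance imbalance, which the planned standard error already covers. Adjustment helps in reading a given sample, but chance imbalance is not a bias over repeated samples.

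The documents report no association of NAS with BMI or diabetes, so the size rests on assumptions. The Section 3.1 filter on diagnosis makes very low baselines less likely, though it sets no value. The regression has no 2-point threshold, so the fact that a subject starting at 2 must reach 0 to count bears on the responder count in Section 3.2 and not on this model.

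Finally, Section 7 presents the regression as an addition to the primary test in a pilot. That limits priority but does not remove the ambiguity in reading its coefficients.

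**Conclusion.** The point holds as a gap in a supporting analysis. The planned model cannot separate a BMI or diabetes effect from a difference in starting NAS. The distortion needs both a fall that depends on the starting score and a baseline NAS that differs by the covariate. With an assumed 1-point gap it is about 0.35 points for a 35% fall and about 0.50 for a 50% fall. At 35% it is within one standard error, and it vanishes if the fall is constant.

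A baseline-adjusted model is informative but not a cure. With a true 1-point gap it can err by about 0.1 to 0.4 points in the opposite direction, so neither model alone is sufficient. A reader might infer that the primary result is compromised. It is not: the endpoint, the paired t-test and the sample size of 20 do not use this regression. Priority is low to moderate.

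**What to change.** In Section 7, keep the planned univariable and multivariable models and add three things.
- One prespecified multivariable model of NAS change on BMI, diabetes and baseline NAS from the placement biopsy, reported beside the planned multivariable model.
- A statement that a BMI or diabetes effect will be interpreted cautiously if the two models disagree, noting that biopsy error in baseline NAS can bias the adjusted coefficient.
- A listing of responder counts (fall of at least 2 points) by baseline NAS.

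Baseline NAS should not be added to the univariable models, which would then no longer be univariable. Reporting mean change at the average baseline NAS adds nothing, because in a single-arm least-squares fit the prediction at average covariate values equals the raw mean change.

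The cost is one residual degree of freedom (17 to 16) in the added model and one more table. No new data, no change to eligibility and no change to sample size are needed.

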8.1 Definitions

Unanticipated Adverse Device Effect (UADE)

A UADE is any serious adverse effect on health or safety or any life-threatening problem or death caused by, or associated with, a device if that effect, problem or death was not previously identified in nature, severity, or degree of incidence in the investigational plan or IDE application (including a supplementary plan or application), or any other unanticipated serious problem associated with a device that relates to the rights, safety, or welfare of subjects.

Adverse Effect (Event)

Any untoward medical occurrence in a subject involved in clinical study of an investigational device; regardless of the causal relationship of the problem with the device or, if applicable, other study related treatment(s).

General Physical Examination Findings

At screening, any clinically significant abnormality should be recorded as a preexisting condition. At the end of the study, any new clinically significant findings/abnormalities that meet the definition of an adverse event must also be recorded and documented as an adverse event.

Hospitalization, Prolonged Hospitalization or Surgery

Any adverse event that results in hospitalization or prolonged hospitalization should be documented and reported as an unanticipated adverse device effect unless specifically instructed otherwise in this protocol. Any condition responsible for surgery should be documented as an adverse event if the condition meets the criteria for an adverse event.

Neither the condition, hospitalization, prolonged hospitalization, nor surgery are reported as an adverse event in the following circumstances:

Post-study Adverse Event

All unresolved adverse events should be followed by the investigator until the events are resolved, the subject is lost to follow-up, or the adverse event is otherwise explained. At the last scheduled visit, the local investigator should instruct each subject to report, to the local investigator, any subsequent event(s) that the subject, or the subject's personal physician, believes might reasonably be related to participation in this study. The local investigator should notify the study regulatory sponsor of any death or adverse event occurring at any time after a subject has discontinued or terminated study participation that may reasonably be related to this study. The sponsor should also be notified if the local investigator should become aware of the development of problems, cancer or of a congenital anomaly in a subsequently conceived offspring of a subject that has participated in this study.

Preexisting Condition

A preexisting condition is one that is present at the start of the study. A preexisting condition should be recorded as an adverse event if the frequency, intensity, or the character of the condition worsens during the study period.

Unanticipated Problems Involving Risk to Subjects or Others (UPIRTSO)

Any unanticipated problem or adverse event that meets all of the following three criteria:

- **Serious:** Serious problems or events that results in significant harm, (which may be physical, psychological, financial, social, economic, or legal) or increased risk for the subject or others (including individuals who are not research subjects). These include: (1) death; (2) life threatening adverse experience; (3) hospitalization - inpatient, new, or prolonged; (4) disability/incapacity - persistent or significant; (5) birth defect/anomaly; (6) breach of confidentiality and (7) other problems, events, or new information (i.e. publications, DSMB reports, interim findings, product labeling change) that in the opinion of the local investigator may adversely affect the rights, safety, or welfare of the subjects or others, or substantially compromise the research data, **AND**
- **Unanticipated:** (i.e. unexpected) problems or events are those that are not already described as potential risks in the protocol, consent document, not listed in the Investigator's Brochure, or not part of an underlying disease. A problem or event is "unanticipated" when it was unforeseeable at the time of its occurrence. A problem or event is "unanticipated" when it occurs at an increased frequency or at an increased severity than expected, **AND**
- **Related:** A problem or event is "related" if it is possibly related to the research procedures.

8.2 Adverse Event Reporting Period

For this study, the study treatment follow-up period is defined from enrollment in the study to 6 months after balloon removal (12 months from balloon insertion). Adverse events will be captured and reported from enrollment to the end of the study treatment follow-up.

8.3 Recording of Adverse Events

Adverse events will be solicited at each study visit or contact with patient. All adverse events will be recorder on the below case report form:

- Subject Study Number/Identifier
- Device information (model and serial number)
- Date of event onset
- Description of the event
- Indication if study treatment was discontinued, or if investigational device was removed
- Subject current status, or if the event was resolved
- Principal Investigator assessment of if the event was serious and justification for determination

- Principal Investigator assessment of causality and relationship to study treatment.

8.4 Sponsor-Investigator Reporting of Unanticipated Adverse Device Effects and Unanticipated Problems

When an adverse event has been identified, the study team will take appropriated action necessary to protect the study participant and then complete the Study Adverse Event Worksheet and log. The sponsor-investigator will evaluate the event and determine the necessary follow-up and reporting required.

The sponsor-investigator will promptly review documented Unanticipated Adverse Device Effects and as necessary shall report the results of such evaluation to FDA within 10 working days and Mayo IRB within 5 working days of initial notice of the effect. Thereafter the sponsor-investigator will submit such additional reports concerning the effect as requested.

8.4.1 Sponsor-Investigator Reporting, Notifying Mayo IRB

The sponsor-investigator will report to the Mayo IRB any UPIRTSOs and Non-UPIRTSOs according to the Mayo IRB Policy and Procedures.

8.4.2 Sponsor-Investigator Reporting: Notifying the FDA

The sponsor-investigator will report to the FDA all unanticipated adverse device effects according to the required reporting timelines, formats and regulations.

The sponsor-investigator will submit a completed FDA Form 3500A to the FDA's Center for Devices and Radiological Health for any observed or reported adverse effect that is determined to be an unanticipated adverse device effect. A copy of this completed form will be provided to all participating sub-investigators. (Note: DSMP)

The completed FDA Form 3500A will be submitted to the FDA as soon as possible and, in no event, later than 10 working days after the sponsor-investigator first receives notice of the adverse effect.

If the results of the sponsor-investigator's follow-up evaluation shows that an adverse effect that was initially determined to not constitute an unanticipated adverse device effect does, in fact, meet the requirements for reporting; the sponsor-investigator will submit a completed FDA Form 3500A as soon as possible, but in no event later than 10 working days, after the determination was made.

For each submitted FDA Form 3500A, the sponsor-investigator will identify all previously submitted reports that that addressed a similar adverse effect experience and will provide an analysis of the significance of newly reported adverse effect in light of any previous, similar report(s).

Subsequent to the initial submission of a completed FDA Form 3500A, the sponsor-investigator will submit additional information concerning the reported adverse effect as requested by the FDA.

Reporting Process

Unanticipated Adverse Device Effect reports will be submitted on FDA Form 3500A. The contact information for submitting reports is:

Food and Drug Administration
Center for Devices and Radiological Health
Document Mail Center - WO66-G609
[name]
[name]

Deviations from the investigational plan

The sponsor-investigator shall notify Mayo IRB (see 21 CFR 56.108(a) (3) and (4)) of any deviation from the investigational plan to protect the life or physical well-being of a subject in an emergency. Such notice shall be given as soon as possible, but in no event later than 5 working days after the emergency occurred. Except in such an emergency, prior approval by the sponsor-investigator is required for changes in or deviations from a plan, and if these changes or deviations may affect the scientific soundness of the plan or the rights, safety, or welfare of human subjects, FDA and IRB notification in accordance with 21 CFR 812.35(a) also is required.

8.5 Unblinding Procedures

Not applicable

8.6 Stopping Rules

- 1 death
- 2 or more severe adverse events or severe unanticipated adverse device effect deemed of enough severity by the primary investigator and co-investigator to stop the study due to safety concerns that can't be mitigated by the study team. In that case the study will not resume until approval is obtained from the FDA and IRB.

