4.4 Early Withdrawal of Subjects

4.4.1 When and How to Withdraw Subjects

Study will be stopped:

- 1 death

- 2 or more severe adverse events or unanticipated adverse device effects deemed of enough severity to stop the study by an independent data safety and monitoring board consisting of three Mayo consultants independent from the study

Patient will be withdrawn from the study:

- Subject safety issues, adverse device effects
- Failure of subject to adhere to protocol requirements
- Disease progression to cirrhosis within the time frame of the study
- Subject decision to withdraw from the study (withdrawal of consent)

Replacement of withdrawn subjects:

If a patient is withdrawn from the study for reasons other than severe adverse events, the intragastric balloon will be removed from the patient at a time that works for the patient and within six months of insertion. The patient will be followed as per the standard clinical protocol for the intragastric balloon to ensure safety. Weight and safety data will be collected until the intragastric balloon is removed. After balloon removal subjected will be followed clinically as per our protocol for additional three months to ensure safety. We will replace up to 5 subjects withdrawn for reasons other than severe adverse events.

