8.7.1 Internal Data and Safety Monitoring Board

The data safety will be monitored directly by the primary investigator.

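### The study stopping rule is stated twice: Section 4.4.1 gives the judgement to an independent board, Section 8.6 gives it to the investigators, and the device-effect threshold may also differ.

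*Combined protocol and SAP*

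**What the plan says.** Section 4.4.1, although headed as a section on withdrawing subjects, opens with a study-level stopping rule. One trigger is a single death. The other is "2 or more severe adverse events or unanticipated adverse device effects deemed of enough severity to stop the study", and that judgement is to be made "by an independent data safety and monitoring board consisting of three Mayo consultants independent from the study".

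Section 8.6, Stopping Rules, repeats the single-death trigger. Its second trigger is "2 or more severe adverse events or severe unanticipated adverse device effect", where the events are "deemed of enough severity by the primary investigator and co-investigator to stop the study" and the reason is "due to safety concerns that can't be mitigated by the study team". It adds that in that case "the study will not resume until approval is obtained from the FDA and IRB". It does not mention a board.

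Section 8.7.1 carries the title of an internal data and safety monitoring board, but its only sentence is: "The data safety will be monitored directly by the primary investigator". The one other reference to a board's output in the safety section is in the definitions in Section 8.1, in a general list of new information: "publications, DSMB reports, interim findings, product labeling change". That list assigns no stopping decision to anyone.

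**The concern.** This rule decides whether an open-label, single-arm device study continues after harm to participants. One version requires that the people making the judgement be independent of the study; the other gives it to the people running the study. After two severe adverse events, a site following Section 4.4.1 would take the matter to three independent consultants, and a site following Section 8.6 would decide among the investigators. Either course follows one section and departs from the other. If the two bodies disagreed, the protocol gives no answer.

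The events that bring the question to a decision-maker may differ as well, because the two sections describe the qualifying device effects differently. Reporting of unanticipated device effects to the IRB and FDA (Sections 8.4 to 8.4.2) applies under either version, but it does not settle who stops the study.

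**Working it through.** The defect is textual. The plan states no figure to reproduce and no event rate is used, so the check sets the two statements side by side and then looks for any other text that joins or ranks them.

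| Element | Section 4.4.1 | Section 8.6 | Result |
|---|---|---|---|
| Death | 1 | 1 | Same |
| Severe adverse events | 2 or more | 2 or more | Same |
| Who judges | Independent board of three consultants | Primary investigator and co-investigator | Differs |
| Device effects that count | Plural, not separately marked severe | Singular, marked severe | Wording differs; effect depends on reading |
| Study team cannot mitigate the concern | Not stated | Stated | 8.6 only |
| Condition for resuming | Not stated | FDA and IRB approval | 8.6 only |

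Count: 2 same + 2 worded differently + 2 in Section 8.6 only = 6.

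**Does other text resolve it?**

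- Section 8.7 makes the sponsor-investigator responsible for overseeing safety but assigns no stopping decision. It points to Section 10 for monitoring and auditing; Section 10 is Ethical Considerations, and monitoring and auditing are in Section 9.
- Sections 9.1 and 9.2 cover monitoring visits, audits and inspections. They assign no stopping decision.
- Section 8.7.1 has a board in its heading and the primary investigator in its text, so it does not resolve the conflict.
- Sections 8.4 to 8.4.2 cover reporting only.

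Nothing found ranks the two versions or says that they operate jointly.

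**What the differences do in practice**

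- (a) *Two severe adverse events.* Both versions reach a judgement, but different people make it. This needs no interpretation.
- (b) *One severe unanticipated device effect.* Section 8.6 is reached if its singular means that one suffices. In Section 4.4.1 the plural after the count of two points to at least two.
- (c) *Two unanticipated device effects not graded severe.* Section 4.4.1 is reached if *severe* does not carry over from adverse events to device effects. Section 8.6 is not reached.

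Cases (b) and (c) depend on readings that the text leaves open. The definition in Section 8.1 does not close them: it describes an unanticipated device effect as *serious*, Section 3.4 grades adverse events for *severity*, and no section says how the two terms relate.

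**The case against.** The strongest reply is that only one clause is truly in conflict. Section 8.6 is the section dedicated to stopping and is the fuller statement, and Sections 8.7 and 8.7.1 also place safety oversight with the investigator. Mitigation and resuming are extra detail on which Section 4.4.1 is silent, and both can be applied without breaking either section. The singular in Section 8.6 may be loose drafting, since the protocol uses singular for plural elsewhere, and the count of two could govern both nouns. Section 4.4.1 also requires that events be judged severe enough to stop the study, so case (c) changes at most which events open a discussion. Finally, neither section claims exclusive authority, so both bodies might hold it.

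Much of this stands. Mitigation and resuming are not contradictions and are counted above only as stated in one place. The device-effect difference is an ambiguity, and cases (b) and (c) concern what opens the judgement rather than what the judgement will be.

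The reply does not remove the main point. No text gives Section 8.6 precedence, and Section 4.4.1 is just as direct that the study will be stopped. Joint authority is conceivable but unstated, and it would leave open what happens if the two bodies disagree. That Sections 8.7 and 8.7.1 lean towards the investigator does not cancel the board named in Section 4.4.1; it leaves that board with a stopping role and no description beyond its size and independence.

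**Conclusion.** The concern holds and must be fixed. The conflict over who decides is explicit and rests on no inference. The difference in qualifying device effects is possible, depending on the readings set out in cases (b) and (c). Two further conditions are stated in one place only. The death trigger and the count of severe adverse events agree. The primary analysis and the sample size are not affected.

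The conclusion assumes that both sections are current text of equal standing, and that no separate document outside the protocol sets the relation between the board and the investigators. Confidence is high on the decision-maker point, which would stand unchanged if the device-effect point were dropped. No view is given on which version is right.

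**What to change.** Reconcile Sections 4.4.1, 8.6 and 8.7.1 into a single rule, stated once and cross-referenced from the other sections. It should give:

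- one named decision-maker, or an explicit statement of how the board and the investigators act together and what happens if they disagree;
- one wording and one count for qualifying device effects, saying whether *severe* applies to them and how it relates to *serious*;
- one position on whether the mitigation condition applies;
- one condition for resuming.

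Make the heading and text of Section 8.7.1 agree. As an editorial matter, correct the pointer in Section 8.7 from Section 10 to Section 9.

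The cost is wording in three sections plus one cross-reference. If the reconciled text keeps a board, its operation must also be described, because Section 4.4.1 gives only its size and independence. The choice between the versions is for the sponsor-investigator.
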